6.1.2. Secondary study parameters/endpoints

To evaluate the preliminary effectiveness of an on average six-week homemonitored prehabilitation program in patients with AAA scheduled for elective AAArepair to improve the preoperative VO2 at the ventilatory anaerobic threshold (VAT). Yet, it is uncertain if diet, SES, frailty score, and other patient characteristics may predict the improvement of fitness within 6 weeks, on average.

Other secondary aims are program feasibility (recruitment rate, adherence, completion rate, drop-out rate, attrition rate, and adverse events); the (preliminary) effect of the program on other cardiopulmonary exercise testing (CPET) values; as well as the effect of the program with the Luscii-app. The individual (preliminary) effect of prehabilitation on other CPET values are evaluated, as well, and the postoperative course in patients after AAA repair; by collecting data on the surgical intervention and postoperative outcomes.

6.1.3. Other study parameters (if applicable)

Other parameters will be monitored, such as the number of complications (MACEs, MALEs, and others), hospital length of stay, number of readmissions, and mortality.

6.2. Randomisation, blinding and treatment allocation

It is not intended to perform randomization in this single-arm intervention study. Included subjects will be followed during their preparation before an AAA repair. These findings will be compared between patients with and without improvement after training (age, ASA, smoking, hypertension, dyslipidemia, diabetes, et cetera).

6.3. Study procedures

Patients with an indication for AAA repair are routinely prepared for this operation with a visit at the anesthesiologist and the cardiologist. After the indication is set, the minimal waiting time for the operation is usually six weeks on average. This gives the

Version number: 4 21 of 41

subject the opportunity to start training. Surgery will not be postponed for this pilot study.

After the indication and informed consent, a questionnaire will be completed with the help of a professional research-nurse, and a cardiologic consultation will be performed. When subjects are fit for training, they will be informed about the use of the home-monitoring device. This will be followed by a visit at physical therapist (Figure 1).

Estimation of costs Aneurysm in motion					
	WZA (40	patients)	Treant (60 p	Totals	
Intake Luscii	€ 32	€ 1.280	€ 32	€ 1.920	€ 3.200
Alert Luscii	€ 14,70	€ 588	€ 14,70	€ 882	€ 1.470
Costs research bureau (30 minutes)	€ 20	€ 800	€ 20	€ 1.200	€ 2.000
	Totaal 1 jaar	€ 2.668		€ 4.002	
Both hospitals					€ 6.670

Table 2: Expected costs in participating hospitals, without insurance costs.

Following these three explanations (home monitoring, questionnaires, and training), the subject will be asked to start their home training during office hours, following a communication with the communication center of the home monitoring (Luscii). After each training and cooling down, parameters should be imported from the homemonitoring device and feedback will be given from the communication center. In case of anomalous measurements, the hospital will be contacted.

	Action	Conditions	Requirement Fit patients	Requirement Unfit patients
Inclusion criteria	Indication AAA repair	Elective repair	Eligible for inclusion	Eligible for inclusion
Inc	Informed consent	Signed	Eligible for inclusion	Eligible for inclusion
	Questionnaire	Various characteristics	One hour	One hour
	Specialist sports medicine	Consultation and CPET	One hour	-
	Cardiologist	Safe to perform training	Questionnaire and CPET	-
		Unsafe	-	Follow up
ıction	Explanation	Home monitoring device	One hour	-
Introduction	First visit physical therapist	At location physical therapist	One hour	-
iks	Daily training at home	Four days a week	Four hours	-
3-9 weeks	Weekly visit physical therapist	Once a week	One hour	-
Postop	Three months after the operation	Outpatient clinic	Ten minutes	Follow up

Table 3: time investment of the included subjects. AAA= aneurysm of the abdominal aorta; CPET= cardiopulmonary exercise test

6.4. Withdrawal of individual subjects

Subjects can leave the study at any time for any reason if they wish to do so without any consequences. The investigator can decide to withdraw a subject from the study for urgent medical reasons.

6.4.1. Specific criteria for withdrawal (if applicable)

Not applicable.

6.5. Replacement of individual subjects after withdrawal

Not applicable

Version number: 4 23 of 41

6.6. Follow-up of subjects withdrawn from treatment

Subjects who withdraw from the study will be followed three months after the AAA repair, when they approve the investigators to do so. This data will be used to compare HLOS, complications, and readmissions.

6.7. Premature termination of the study

Although recent literature acknowledges the safety of training in AAA patients, this study will be terminated when more than 10% of the included subjects die in course of their preparation of the operation.

A termination of the study will be advocated when more than half of the included subjects withdraw. When this is the case, it will be considered whether the training program is too heavy, or the condition of the patients is not sufficient to exercise the way they are asked to do.

7. SAFETY REPORTING

7.1. Temporary halt for reasons of subject safety

In accordance with the WMO, the sponsor will suspend the study if there is sufficient ground that continuation of the study will jeopardize subject health or safety. The sponsor will notify the accredited METC without undue delay of a temporary halt including the reason for such an action. The study will be suspended pending a further positive decision by the accredited METC. The investigator will take care that all subjects are kept informed.

7.2. AEs, SAEs and SUSARs

7.2.1. Adverse events (AEs)

Adverse events are defined as any undesirable experience occurring to a subject during the study, whether or not considered related to the intervention. All adverse events reported spontaneously by the subject or observed by the investigator or staff will be recorded.

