Several trials have established exercise training to be safe in people with AAA and training does not seem to influence aneurysm growth (8-11). Professional supervision (e.g., physical therapy and in-hospital aerobic exercise training) is expensive. Home-based monitoring of exercising patients with AAA is less expensive, and device handling by patients has been positively evaluated before (12).

This study is designed to investigate whether patients with AAA can improve their preoperative aerobic fitness during 3- to 9-week (6 weeks on average) training program. It is primarily designed to evaluate which patients benefit most from this program, based on three outcome measures: initial fitness (CPET), BMI and age. Home training will be performed with home-monitoring and weekly support by a physical therapist.

A successful six-week training program is a true investment, and some patients will not be able to benefit from it. At this point we are unable to select patients who will benefit most. Improvement of aerobic fitness probably depends on a combination of patient specific factors, e.g., age and sex, comorbidity, aerobic fitness at the start of the training, dietary habits, comorbidity, SES, frailty index, ASA-score, physical strength, and the available social support. Training specific factors play a role as well, such as the number of prescribed training sessions, intensity, and the duration. This study is designed to select patients who will benefit most from training, based upon their initial fitness, their BMI and their age. Patients with an AAA and an indication for operative repair were often male smokers, with high blood pressure, and lipid profiles (1). Depending on their diligence, recruitment rate, adherence, completion, drop-out, and attrition rate, will be important. These rates will be evaluated in relation to SES and other characteristics. During training, patients will be supported with dietary substitutes, in order to maintain an anabolic condition (13). Due to the training at home, the Luscii app (CE-certificate 0476) enables patients to ask questions and this might stimulate them to start training, under the suggestion to be observed by the call center.

OBJECTIVES

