Following the explanation, patients have their intake with a physical therapist. The patients able to perform training, will be prescribed a personalized exercise program and will be followed by a local physical therapist. This includes a training scheme for exercises at home (Appendix 2). They will be asked to train at home and once a week at the physical therapist, check their vital sings with the pulse oximeter and de SMM, and communicate these vital

Version number: 4

signs with the Luscii app to a call center Altide. In case of previously set limitations, this call center will contact the hospital (Appendix 3).

Home-monitored training

All eligible patients will participate in a three-to-nine-week (average of six weeks), partly supervised, home-monitored training program prior to elective AAA-repair. The second CPET measurement is planned after the training program. Training frequency during the prehabilitation will be five sessions per week including a weekly evaluation by the physical therapist. Training sessions at home are prepared and should be able to be performed without extra adjuncts (see below). Before and after home-monitored training sessions without a physical therapist, subjects communicate oxygen saturation, heartrate, blood pressure, number of steps (nS), and number of smoked cigarettes through the Luscii app. According to these measurements, automatic advises will be given through the app (Appendix 3).

To evaluate a difference after the average of six weeks, subjects visit the specialist in sports medicine a second time to perform a CPET. Depending on the performance of patients in relation to the improvement in this second CPET, a subdivision of an improved and a stable (not improved) group will be made. It is expected that improved patients will show an increase of their VO2 at VAT of 1,5 ml/kg/min or more.

Three months after surgery, monitoring is complete, and preoperative patient characteristics of the groups will be compared.

Home-monitored exercises

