Four times a week subjects perform exercises at home, preceded and followed by communication of preset parameters through the Luscii app. These exercises include stair-climbing and sit-to-stand exercises (high-intensity), as well as outdoor cycling, outdoor walking, and outdoor running (moderate intensity). The combination will be assembled in close collaboration between the physical therapist and the specialist in sports medicine, under the responsibility of the principal investigator. Through registration and monitoring activities by the patient, the physical therapist will be able to advise activities performed at home. The physical therapist will discuss these findings with the patient on a weekly base and adjust the scheme in relation to physical improvement.

Once a week subjects perform a steep ramp test performance to estimate aerobic fitness, under the supervision of the physical therapist. This test is used to optimize training intensity of the interval and endurance training sessions, as well as to monitor progression.

Nutritional supplementation

Version number: 4

To support muscle protein synthesis, participants will be provided with protein supplementation immediately following exercise and (approximately 30 minutes) before sleep, providing a standard dosage of 30 g of a high-quality (whey and casein) protein that contains at least 10 g of essential amino acids, of which 2-3 g Leucine. Since vitamin D is associated with muscle mass and muscle strength. It will be supplemented daily according to guidelines of the Health Council of the Netherlands (10 μ g for woman aged 50-69 years, for men <70 years and women <50 years with colored skin and/or little sun exposure, and 20 μ g for women and men aged 70 years or older)(14, 15). To prevent patients from having a deficiency of vitamins and minerals below recommended doses before surgery, all other vitamins and minerals are supplied in a multivitamin/mineral supplement containing 50% of the recommended daily allowance (13).

[figure not shown]

Figure 1: flow chart (https://app.diagrams.net) concerning the references of patients. FT= physical therapy, CPET= cardiopulmonary exercise test, HLOS= hospital length of stay.

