8.2. Secondary study parameter(s)

To measure if patients with an indication for AAA-repair can improve their VO2 at VAT. The second measurement will be performed after a three to nine week training program, using the advice of a specialist in sports medicine, consults of a physical therapist and eHealth monitoring. To evaluate the effectiveness of the, on average, six-week home-monitored prehabilitation program, the difference in the VO2 at the ventilatory anaerobic threshold before the start of the training and after an average six weeks of prehabilitation will be analyzed using a paired samples t-test or Wilcoxon signed rank test, as appropriate. A repeated measurements analysis (mixed models in SPSS) will be performed to assess changes over time in continuous variables. P values <0.05 will be considered statistically significant. Modifiable factors will be analyzed as well, such as dietary habits, social economic status, frailty score, and other information collected in the questionnaires.

To evaluate the feasibility of the average six-week home-monitored prehabilitation program, adherence or compliance, adverse events, motivation, and patient appreciation will be described by use of descriptive statistics. Descriptive statistics will be used to present data on perioperative variables and postoperative progress.

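### Adverse events are a feasibility endpoint but are collected only when volunteered or observed, so non-serious events in the mostly home-based training are likely to be under-counted by an unknown amount

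*Protocol*

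**What the plan says.** **Definition and collection.** Section 7.2.1 defines adverse events broadly: "Adverse events are defined as any undesirable experience occurring to a subject during the study, whether or not considered related to the intervention". It then limits what reaches the data: "All adverse events reported spontaneously by the subject or observed by the investigator or staff will be recorded".

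**Use as an outcome.** Section 6.1.2 lists adverse events among the feasibility outcomes: "program feasibility (recruitment rate, adherence, completion rate, drop-out rate, attrition rate, and adverse events". Section 8.2 says how they will be summarised: "adherence or compliance, adverse events, motivation, and patient appreciation will be described by use of descriptive statistics".

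**Where training happens.** Section 1 (Home-monitored training) gives the frequency: "Training frequency during the prehabilitation will be five sessions per week including a weekly evaluation by the physical therapist". Section 1 (Home-monitored exercises) adds: "Four times a week subjects perform exercises at home, preceded and followed by communication of preset parameters through the Luscii app".

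**What is transmitted.** Around the home sessions, "subjects communicate oxygen saturation, heartrate, blood pressure, number of steps (nS), and number of smoked cigarettes through the Luscii app" (Section 1). The Appendix 1 log has columns for date, times, saturation, blood pressure and whether the data were sent. The automated replies in Appendix 3 respond to saturation, pulse, blood pressure, steps and cigarettes.

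**Other contacts.** The Introduction and rationale says that "the Luscii app (CE-certificate 0476) enables patients to ask questions". A call centre contacts the hospital when preset limits are met (Section 1) or readings are abnormal (Section 6.3). The therapist reviews the home activity with the patient each week (Section 1). A second cardiopulmonary exercise test (CPET) and an outpatient visit three months after the operation follow (Section 1 and Table 3).

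**The concern.** The definition is wide and the collection route is narrow. Of the two routes in Section 7.2.1, direct observation cannot work during a home session, because no study staff are there. What remains is the patient deciding, unprompted, that a sore knee, a dizzy spell or a stumble is worth mentioning.

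How events are elicited is a data-collection rule that the protocol itself fixes. A statistical analysis plan could not repair it, because events that were never asked about cannot be recovered in the analysis.

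At stake is the reading of one feasibility result. The protocol expects training to do no harm and foresees a possible larger trial (Section 7.5). A short list of events would be taken as support for that, although it would partly reflect how the events were collected. The progress reporting in Sections 7.5 and 10.4 names serious adverse events and operative complications. For non-serious training events, Section 7.2.1 is the only collection rule the document describes.

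**Working it through.** The protocol states no expected adverse-event rate and no capture share, so there is no figure of its own to reproduce. The check has three parts.

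**1. Share of sessions without study staff.** Inputs from Section 1: five sessions a week, four at home and one with the therapist.

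- Share at home = 4 / 5 = 80%.
- Per patient over 3, 6 or 9 weeks: 4 × weeks = 12, 24 or 36 home sessions, against 3, 6 or 9 therapist visits.
- Group total, assuming 80 trained patients (100 × (1 − 0.20), using the exclusion rate in Section 2.4) who all complete six weeks: 80 × 6 × 4 = 1,920 home sessions and 80 × 6 × 1 = 480 therapist sessions. The 20% drop-out in Section 2.4 would lower both totals. It would not change the scheduled 80%.

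Section 3.1 can be read as home training on every weekday plus the therapist visit, which would give 5 / 6 = 83%. The passages should be reconciled, but the point is the same under either reading.

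**2. Is any contact an adverse-event enquiry?**

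| Contact or record | What the protocol describes | Adverse-event question described? |
|---|---|---|
| Routine app entry before and after a home session | Five numeric items | No |
| App questions from the patient | Initiated by the patient | No; this is still spontaneous report |
| Appendix 1 home log | Times, saturation, blood pressure, sent or not | No |
| Appendix 3 automated replies | Triggered by readings, steps and cigarettes | No |
| Call centre | Reacts to limits and abnormal readings | No |
| Weekly therapist visit | Review of home activity, scheme adjustment, steep ramp test | No; it is also not stated whether a local therapist counts as staff |
| Second CPET | Change in fitness | No |
| Three-month visit | Outpatient check | No |

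Several of these are chances to volunteer or notice an event. None turns the passive rule into an active one.

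**3. What incomplete capture would do (illustration only).** Observed proportion = true proportion × share captured. Both inputs are assumptions. The number of patients observed is out of 80.

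| True proportion | 50% captured | 70% captured | 90% captured |
|---|---|---|---|
| 10% (8 patients) | 5% (4.0) | 7% (5.6) | 9% (7.2) |
| 20% (16 patients) | 10% (8.0) | 14% (11.2) | 18% (14.4) |
| 40% (32 patients) | 20% (16.0) | 28% (22.4) | 36% (28.8) |

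The shortfall is zero only if capture is complete. The same condition applies to a count of zero: with 0 of 80 patients affected, the one-sided 95% upper limit is 1 − 0.05^(1/80) = 3.7%, and that limit is valid only if every such event would have been recorded.

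**The case against.** The strongest reply is that patients in this study have many contacts. Home sessions are remotely supervised, spouses or caregivers are instructed in the devices, abnormal readings reach the hospital, many automated replies send the patient to the therapist, and the therapist sees each patient weekly. The result is only descriptive, and the case report form, which is not shown, might already carry a prompt.

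Much of this stands, and it rules out several stronger readings:

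- A reader might infer that the app carries nothing but numbers. The Introduction says patients can ask questions through it; only the routine entries are numeric.
- A reader might infer that patients exercise with nobody there. The documents support only that no study staff are present.
- A reader might equate the 80% of sessions at home with 80% of events lost. An event at home can still be mentioned at the next weekly visit, so the share of sessions is not a share of events.
- A reader might say the result will certainly be too low, or divide the 3.7% limit by a guessed capture share. The first is too definite, and the second only returns the guess.
- A reader might blame the lack of a control arm. A control arm under the same passive rule would not reveal under-counting either.

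What does not stand is that the contacts settle the matter, since none is described as asking about adverse events. A prompt in an unseen form would also differ from the rule in Section 7.2.1, which refers to spontaneous reports and observation. Section 7.2.1 would then still need amending.

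**Conclusion.** The concern holds in a limited form. Section 7.2.1 fixes passive capture for a named feasibility endpoint in a programme with 80% of its sessions at home, and no described contact includes an adverse-event enquiry. Under-counting of non-serious events is likely, and the documents do not allow its amount to be estimated. The table of assumed capture shares shows the direction and the mechanism only.

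The consequences are bounded. Serious events such as death or hospital admission are less likely to be missed. Adverse events are described without a test or threshold, and the termination criteria in Section 6.7 rest on deaths and withdrawals. The statement of very low risk in Section 11.2 is a prior judgement that draws on earlier studies, not a conclusion from this trial's count. This is a cheap improvement to how one endpoint can be interpreted. It does not show that the trial is unsafe or that its primary result is affected.

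**What to change.** In Section 7.2.1, replace the passive rule with one fixed open question on new symptoms, injuries or events since the last contact. Specifically:

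- Ask it at every existing weekly therapist visit, at the second CPET and at the postoperative visit. Section 9.2 gives 30 days of follow-up, while the Summary, Section 1 and Table 3 give three months, so the end of the observation window must be reconciled first.
- Record each answer in the case report form, including an answer of none.
- State that the local therapist forwards the answers to the study team, because the protocol does not say whether local therapists count as staff.
- Report solicited and spontaneous events separately, with the number of contacts at which the question was asked.

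A yes/no complaint item in the app entry after each session is an optional extra. It is not part of the minimum change, because someone would have to handle every positive answer and Table 2 shows that app alerts carry a cost.

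The cost is slightly more recording by the therapist and a step to forward the answers; no new visit is needed. The downside is more minor events on record and a less favourable adverse-event rate.

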7.2.2. Serious adverse events (SAEs)

A serious adverse event is any untoward medical occurrence or effect that:

- results in death.
- is life threatening (at the time of the event);

Version number: 4 24 of 41

- requires preoperative hospitalization or prolongation of existing inpatients' hospitalization.
- results in persistent or significant disability or incapacity.
- requires urgent surgical intervention; or
- any other important medical event that did not result in any of the outcomes listed above due to medical or surgical intervention but could have been based upon appropriate judgement by the investigator.

An elective hospital admission or urgent re-admission will not be considered as a serious adverse event.

The investigator will report all SAEs to the sponsor without undue delay after obtaining knowledge of the events.

The sponsor will report the SAEs that result in death or are life threatening through the web portal *ToetsingOnline* to the accredited METC that approved the protocol, within 7 days of first knowledge for SAEs followed by a period of maximum of 8 days to complete the initial preliminary report. All other SAEs will be reported within a period of maximum 15 days after the sponsor has first knowledge of the serious adverse events.

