Intervention: Patients who signed informed consent (IC) for this study must fill out a questionnaire, with the assistance of a research nurse and perform a cardiopulmonary exercise test (CPET). Patients rejected from training will be excluded. This is evaluated by the cardiologist and the specialist in sports medicine. Subjects fit for training start with home monitoring (pulse oximeter and sphygmomanometer) under the remote supervision of a physical therapist. All patients will be supported with dietary substitution to avoid a catabolic condition preceding the operation. Before and after three-to-nine-week (on average six weeks) training program, subjects are evaluated by a specialist in sports medicine, to evaluate CoF with a CPET. All patients will be followed until three months postoperative.

Main study parameters/endpoints: The main endpoint is the analysis of patients who improve from training compared to patients who do not improve from training. Secondary endpoints are:

- change in oxygen uptake (VO2) at the ventilatory anaerobic threshold (VAT) after the training program.
- program feasibility (recruitment rate, adherence, completion rate, drop-out rate, attrition rate, and adverse events).
- the (preliminary) effect of the program on other cardiopulmonary exercise testing (CPET) values, e.g., VO2 at peak exercise, oxygen uptake efficiency slope, and response profiles, as well as strength improvement.
- Postoperative events will be compared in relation to the subgroup analysis of patients benefiting from training or not.

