9.2. Recruitment and consent

At the indication for AAA repair, patients will be informed by the treating vascular surgeon. Patients will receive an information document from their treating physician. Eligible subjects receive an appointment with the (co)investigator within one week. When they agree during an appointment with the (co)investigator, patients need to sign a declaration of informed consent. Eligible patients will be given a minimum of 24 hours, and a maximum of 2 weeks, to determine participation. When informed consent is signed, all subjects will complete the questionnaire and will perform a CPET. Bases upon the result of these tests the cardiac evaluation is made, if necessary complemented by other diagnostics. After training and during their surgery, patients will be followed until 30 days hereafter (Figure 1).

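### Section 7.2.2 excludes every urgent re-admission from the SAE definition, against its own seriousness criteria, and postoperative follow-up is given as both 30 days and three months

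*Protocol*

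**What the plan says.** Protocol section 7.2.2 makes an event serious if it is fatal, life threatening or disabling, if it "requires preoperative hospitalization or prolongation of existing" inpatient stay, or if it "requires urgent surgical intervention". A last criterion leaves other important events to the investigator's judgement. The section then closes the definition with: "An elective hospital admission or urgent re-admission will not be considered as a serious adverse event". Fatal and life-threatening SAEs go to the ethics committee within 7 days and all others within 15 days.

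Section 7.4 runs SAE reporting to the end of the study. Section 10.5 sets that end at the point where the last patient has finished the study procedures.

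On follow-up after surgery, the Summary says "All patients will be followed until three months postoperative", and section 1 says "Three months after surgery, monitoring is complete, and preoperative patient characteristics of the groups will be compared". Table 3 in section 6.3 has an outpatient visit at three months, and section 6.6 follows consenting withdrawn subjects for three months. Section 9.2 says instead that "patients will be followed until 30 days hereafter".

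**The concern.** Exempting elective admissions makes sense, because every subject is admitted for a planned repair. Joining urgent re-admissions to that exemption, with no limit by cause, severity, period or relation to training, takes out events that the list above it has just put in. This is a multicentre study. A hospital that applies the closing sentence and a hospital that applies the criteria would handle the same event differently.

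What is at stake is mainly how events are classified and how fast they are reported. The trial has no DSMB (section 7.5) and no annual safety report (section 7.3). The 7- and 15-day SAE reports are its expedited, event-level route to the ethics committee. The annual progress report (section 10.4) includes SAEs, so a narrowed definition carries through to it. The two termination triggers in section 6.7 are deaths during preparation above 10% and withdrawal of more than half of the subjects, and neither responds directly to serious non-fatal events.

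The follow-up conflict is a separate matter. Complications, re-admissions and mortality are study parameters (sections 6.1.3 and 6.6), and their counts depend on how long patients are observed.

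**Working it through.** There is no planned figure to reproduce. The check sets the statements side by side.

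**SAE definition (section 7.2.2)**

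| Type of urgent re-admission | By the listed criteria | By the closing sentence | Result |
|---|---|---|---|
| Fatal | SAE | not an SAE | contradiction |
| Life threatening | SAE | not an SAE | contradiction |
| Leaves lasting disability | SAE | not an SAE | contradiction |
| Needs urgent surgery | SAE | not an SAE | contradiction |
| Unplanned, before the operation | SAE (preoperative hospitalisation) | not an SAE | contradiction |
| After the operation, meeting no other criterion | not an SAE | not an SAE | consistent |

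The conflict covers the first five rows. The fifth falls in the training period, when harm from the exercise programme would be expected to show. The sixth row is not a contradiction, because the hospitalisation criterion covers only preoperative admission or a prolonged stay.

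**What remains if the closing sentence is followed**

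- Recording as an adverse event: kept. Section 7.2.1 records all reported or observed events.
- Counting as a re-admission: kept. Section 6.1.3 collects re-admissions in their own right.
- Operative complications in the annual progress report: kept (section 7.5).
- 7- or 15-day report: lost (section 7.2.2).
- SAE entry in the annual progress report: lost (section 10.4).

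**Follow-up length**

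- Three months: Summary, section 1, Table 3 and section 6.6.
- 30 days: section 9.2.
- Taking three months as 365 / 4 ≈ 91 days, the difference is 91 − 30 = 61 days, and 61 / 91 ≈ 67% of the longer window.

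**Link to SAE reporting**

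The 30-day phrase does not itself set the reporting window, which runs to the end of the study (section 7.4). If the last study procedure is the end of postoperative follow-up in the last patient, operated on at day L, the study ends at about L + 30 or L + 91. The closing date then moves by 61 days. The shorter reading leaves less than three months of reporting only for patients operated on after day L − 61, since (L + 30) − (L − 61) = 91. The effect on SAE reporting is therefore indirect and limited.

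**The case against.** The strongest case on the other side is that little is lost. All adverse events are recorded and followed until resolved or stable, re-admissions are collected separately, and operative complications reach the ethics committee every year. A sensible investigator could report a life-threatening re-admission under that criterion despite the closing sentence. The sponsor must also suspend the study if safety is in doubt (section 7.1). The primary comparison rests on the preoperative change in VO2 at the VAT, and postoperative data are only described, so neither conflict touches the primary analysis.

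Most of this stands, and it rules out several stronger readings that a reader might infer:

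- *Serious events will go unreported.* The documents support only that some may escape expedited reporting and SAE classification.
- *Adverse-event and re-admission counts are biased downwards by the exclusion.* They are not, because neither count depends on the SAE label.
- *Limiting the hospitalisation criterion to the preoperative period is an error.* The intervention ends before surgery, so this is an arguable design choice.
- *A number of lost SAEs can be given.* The protocol states no re-admission rate. Multiplying an assumed rate by the number trained would also count uncomplicated postoperative re-admissions, which meet no hospitalisation criterion in any case.

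It could also be argued that re-admission was meant only as return after discharge from the repair. The sentence does not say so, and that reading would resolve only the preoperative case.

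The objection does not remove the contradictions. Relying on investigators to disregard a written exclusion is no substitute for a consistent definition. Section 9.2 cites Figure 1, which is not visible in the text reviewed, but a figure could not make both follow-up lengths true.

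**Conclusion.** Both contradictions hold as a matter of text and rest on no outside figure. The SAE definition cannot be applied consistently to urgent re-admissions that meet another listed criterion or occur before the operation. On a literal reading these may miss the 7- and 15-day reports and the SAE count in the annual progress report, though not the adverse-event or outcome records. How many events this concerns is unknown.

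The follow-up conflict leaves about 61 of 91 days, or two thirds of the longer window, undefined for complications, re-admissions and mortality. It bears on SAE reporting only through the end-of-study date, assuming that postoperative follow-up is the last study procedure. The primary analysis is unaffected. The wording still needs correcting, because the definition governs expedited safety reporting in a trial with no DSMB.

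**What to change.** In section 7.2.2, remove urgent re-admission from the closing sentence, so that only elective or planned admissions are exempt. Alternatively keep it and add that any re-admission meeting a listed criterion is an SAE. Either wording removes the contradiction without changing the preoperative limit in the hospitalisation criterion.

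Reconcile the 30 days in section 9.2 with the three months in the Summary, section 1, Table 3 and section 6.6, and use one length throughout, so that the observation period and the end of study in section 10.5 have one meaning.

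The cost is a short protocol amendment and a few more SAE reports. The sample size and the primary analysis do not change.
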